12.5 Statistical Analysis Plan

Patient demographics and baseline disease characteristics will be summarized using descriptive statistics. For continuous variables, descriptive statistics such as number, mean, standard deviation, standard error,

median (range) etc. will be provided. For categorical variables, patient counts and percentages will be provided.

CR rate after Induction therapy will be estimated by the proportion of response-evaluable patients achieving CR after Induction therapy, along with the 95% exact binomial confidence interval. ORR during protocol therapy will be similarly estimated. PFS and OS will be estimated using the product-limit method of Kaplan and Meier along with the Greenwood estimator of standard error; 95% confidence interval will be constructed based on log-log transformation. Median PFS/OS will be estimated when available. Observed toxicities of Induction therapy and Maintenance therapy will be summarized by type, severity, and attribution.

For the exploratory objectives, summary statistics and graphics will be used to describe the T cell population and function measures, MRD status, and other correlative analyses. Exploratory correlative analysis will be used to explore the association between the MRD status or gene expression/mutation profiles and clinical outcomes.

13.0 DATA HANDLING, DATA MANAGEMENT, RECORD KEEPING

13.1 Source Documents

Source documents are original documents, data, and records (e.g., medical records, pharmacy dispensing records, recorded data from automated instruments, laboratory data) that are relevant to the clinical trial. The Investigator or their designee will prepare and maintain adequate and accurate source documents. These documents are designed to record all observations and other pertinent data for each patient enrolled in this clinical trial. Source documents must be adequate to reconstruct all data transcribed onto the case report forms.

13.2 Data Capture Methods and Management

Data for this trial will be collected using City of Hope's electronic capture system (EDC) that is compliant with 21 CFR Part 11.

Study personnel will enter data from source documents corresponding to a subject's visit into the protocol-specific electronic Case Report Form (eCRF).

13.3 Case Report Forms/Data Submission Schedule

The Investigator is responsible for all information collected on subjects enrolled in this study. All data collected during the course of this study must be reviewed and verified for completeness and accuracy by the Investigator. All case report forms must be completed by designated study personnel. The completed case report forms must be reviewed, signed and dated by the Investigator or designee in a timely fashion.

All data will be collected using electronic data collection, stored as indicated in [Section 13.2](#), and will be submitted according to the timelines indicated in [Table 13.3](#).

Table 13.3 Data Submission Schedule

Form	Submission Timeline
Eligibility Checklist	Complete prior to registration
On Study Forms	Within 14 calendar days of registration
Baseline Assessment Forms	Within 14 calendar days of registration
Treatment Forms	Within 10 calendar days of treatment administration
Adverse Event Report Forms	Within 10 calendar days of AE assessment/notification

Form	Submission Timeline
Response Assessment Forms	Within 10 calendar days of the response assessment
Other Assessment Forms (concomitant medications)	Within 10 calendar days of the assessment
Off Treatment/Off Study Forms	Within 10 calendar days of end of treatment/study
Follow up/Survival Forms	Within 14 calendar days of the follow up activity

13.4 Regulatory Records

The Investigator will maintain regulatory records, including updating records in accordance with Good Clinical Practice guidelines and FDA regulations.

14.0 REPORTING OF ADVERSE EVENTS, UNANTICIPATED PROBLEMS & OTHER EVENTS OF INTEREST

The research team is responsible for classifying adverse events (AEs) and unanticipated problems (UPs) as defined in the relevant regulations and reporting to all applicable parties, including but not limited to the COH IRB, DSMC, Food and Drug Administration (FDA), National Institutes of Health (NIH) and other collaborators, e.g., pharmaceutical companies. The research team is responsible for the continued monitoring and tracking of all AEs in order to ensure non-reportable events are reviewed and monitored and do not rise to a reporting level.

14.1 Assessment of Adverse Events

The site Investigator will be responsible for determining the event name, and assessing the severity (i.e., grade), expectedness, and attribution of all adverse events as applicable per the [City of Hope Clinical Research Adverse Event and Unanticipated Problem policy](#) (available from the DCC). Adverse events will be characterized using the descriptions and grading scales found in NCI CTCAE v5.0. A copy of the scale can be found at:

https://ctep.cancer.gov/protocoldevelopment/electronic_applications/ctc.htm.

The following definitions will be used to determine the causality (attribution) of the event to the study agent or study procedure.

- **Unrelated** – The event is clearly NOT related to study treatment, and is clearly related to other factors such as the participant's clinical state, other therapeutic interventions, or concomitant medications administered to the participant.
- **Unlikely** – The event is unlikely related to the study treatment, and is most likely related to other factors such as the participant's clinical state, other therapeutic interventions, or concomitant drugs.
- **Possible** – The event may be related to study treatment, as it follows a reasonable temporal sequence from the time of drug administration, but could have been produced by other factors such as the participant's clinical state, other therapeutic interventions, or concomitant drugs.
- **Probable** – The event is most likely related to the study treatment, as it follows a reasonable temporal sequence from the time of drug administration and a known response pattern to the study drug, and is unlikely related to the participant's clinical state, other therapeutic interventions, or concomitant drugs.

- **Definite** – The event is clearly related to the study treatment, as it follows a reasonable temporal sequence from the time of drug administration and a known response pattern to the study drug, and is not reasonably explained by other factors such as the participant's condition, therapeutic interventions, or concomitant drugs.

14.2 Adverse Events of Special Interest (AESI)

Adverse Events of Special Interest (AESI) are events that may not typically be considered to meet the regulatory criteria for expedited reporting, but that for a specific protocol are being reported via expedited means in order to facilitate the timely review of safety data and narrative. It can be e. g. a non-serious non-specific start of an event, which may be an early manifestation of a serious potential risk.

14.2.1 Ventricular arrhythmias

Ventricular arrhythmias (e.g., ventricular extrasystoles, ventricular tachycardia, ventricular arrhythmia, ventricular fibrillation, etc.) are adverse events of special interest (AESIs) for participants exposed to acalabrutinib, and must be reported to AstraZeneca expeditiously, irrespective of regulatory seriousness criteria or causality (Sections [14.5](#) and [14.7](#)).

14.2.2 Secondary Malignancy

A secondary malignancy is a cancer caused by treatment for a previous malignancy (e.g., treatment with investigational agent/intervention, radiation or chemotherapy). A secondary malignancy is not considered a metastasis of the initial neoplasm.

Refer to [Section 14.7](#) for guidelines on reporting secondary malignancies to the industry partners.

14.2.3 Abnormal Liver Function Tests

Cases where a subject shows elevations in liver biochemistry may require further evaluation and occurrences of AST or ALT $\geq 3 \times \text{ULN}$ together with total bilirubin $\geq 2 \times \text{ULN}$ should be reported to AstraZeneca expeditiously (Sections [14.5](#) and [14.7](#)).

14.3 Overdose and Pregnancies

14.3.1 Overdose

Study drug overdose is the accidental or intentional use of the drug in an amount higher than the dose being studied. An overdose or incorrect administration of study drug is not an AE unless it results in untoward medical effects.

Any study drug overdose or incorrect administration of study drug should be noted on the appropriate CRF even if not associated with an AE. All AEs associated with an overdose or incorrect administration of study drug should be recorded on the CRF.

Any accidental or intentional overdose with ublituximab or umbralisib that is symptomatic, even if not fulfilling a seriousness criterion, is to be reported to TG Therapeutics as indicated in Sections [14.5](#) and [14.7](#) on an SAE form, and following the same process described for SAEs.

If a study drug overdose occurs, the subject should stop study drug dosing and be clinically monitored as appropriate, managing symptoms/side effects that may occur.

For any participant experiencing an acalabrutinib overdose, observation for any symptomatic side effects should be instituted, and vital signs and biochemical and hematological parameters should be followed

closely (consistent with the protocol or more frequently, as needed). Appropriate supportive management to mitigate adverse effects should be initiated. If the overdose ingestion is recent and substantial, and if there are no medical contraindications, use of gastric lavage or induction of emesis may be considered. Refer to Sections [14.5](#) and [14.7](#) for guidelines on reporting overdose of acalabrutinib to AstraZeneca.

14.3.2 Pregnancies

14.3.2.1 *Female participants:*

Pregnancies and suspected pregnancies (including a positive pregnancy test regardless of age or disease state) of a female participant occurring after the participant receives the first dose of protocol therapy up to 2 days post-last dose of acalabrutinib and 30 days post-last dose of ublituximab or umbralisib are considered immediately reportable events. **Protocol therapy is to be discontinued immediately. The pregnancy, suspected pregnancy, or positive pregnancy test must be reported to the Study PI and the DCC immediately within 24 hours of awareness (Sections 14.5.1.1 and 14.5.1.2).** The female subject may be referred to an obstetrician-gynecologist (preferably one with reproductive toxicity experience) or another appropriate healthcare professional for further evaluation.

The Investigator should make every effort to follow the female participant until completion of the pregnancy per institutional policies, and should notify the Study PI.

Abnormal pregnancy outcomes and neonatal deaths that occur within 28 days of birth should be reported as an SAE per expedited reporting guidelines. Any infant death after 28 days that the Investigator suspects is related to the in utero exposure to protocol therapy should also be reported as an SAE per expedited reporting guidelines. The Study PI or designee will subsequently inform AstraZeneca and TG therapeutics ([Section 14.7](#)).

14.3.2.2 *Male participants:*

If a female partner of a male participant becomes pregnant, the male participant should notify the Investigator, and the pregnant female partner should be advised to call their healthcare provider immediately. In the event a participant's partner becomes pregnant, the pregnancy should be reported to AstraZeneca and TG Therapeutics ([Section 14.7](#)).

The Investigator should make every effort to follow the outcome of the pregnancy per institutional policies, and should notify the Study PI.

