- Measurable disease by CT or PET/CT scan with one or more sites of disease \geq 1.5 cm in longest dimension (including splenomegaly), or bone marrow involvement with or without malignant lymphocytosis.
- ECOG \leq 2.
- Adequate hematological, renal, and hepatic function.
- Adequate coagulation.
- LVEF \geq 40%.
- Women of childbearing potential: negative serum pregnancy test.
- Agreement by females and males of childbearing potential to use a highly effective method of birth control or abstain from heterosexual activity for the course of the study through at least 2 days after the last dose of acalabrutinib for females, and at least 4 months after the last dose of ublituximab or umbralisib for both men and women.

Main Exclusion Criteria

- Subjects for whom the goal of therapy is tumor debulking before stem cell transplant.
- Chronic use of corticosteroids \geq 20 mg/day (short-term use of steroids $<$ 14 days is allowed).
- Major surgical procedure within 28 days of start of protocol therapy. Note: If a subject had major surgery, they must have recovered adequately from any toxicity and/or complications from the intervention before the first dose of study drug.
- Known history of hypersensitivity or anaphylaxis to study drug(s) including active product or excipient components.

- Concurrent participation in another therapeutic clinical trial.
- History of prior malignancy. Exceptions include malignancy treated with curative intent and no known active disease present for \geq 2 years prior to initiation of protocol therapy; adequately treated non-melanoma skin cancer or lentigo maligna (melanoma in situ) without evidence of disease; adequately treated in situ carcinomas (e.g., cervical, esophageal, etc.) without evidence of disease; asymptomatic prostate cancer managed with “watch and wait” strategy.
- Uncontrolled AIHA (autoimmune hemolytic anemia) or ITP (idiopathic thrombocytopenic purpura).
- Requires treatment with proton pump inhibitors (e.g., omeprazole, esomeprazole, lansoprazole, dexlansoprazole, rabeprazole, or pantoprazole). Subjects receiving proton pump inhibitors who switch to H2-receptor antagonists or antacids are eligible for enrollment to this study.
- Requires treatment with a strong cytochrome P450 3A4 (CYP3A4) inhibitor/inducer.
- Requires or receiving anticoagulation with warfarin or equivalent vitamin K antagonists.

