12. Creatinine clearance of ≥ 30 mL/min per 24 hour urine test or the Cockcroft-Gault formula or $\text{CrCl} = \frac{(140-\text{age}) \times \text{actual body weight (kg)}}{72 \times \text{serum creatinine (mg/dL)}} \quad (\times 0.85 \text{ for females})$ 
Or
 $\text{CrCl} = \frac{(140-\text{age}) \times \text{actual body weight (kg)}}{0.8136 \times \text{serum creatinine (umol/L)}} \quad (\times 0.85 \text{ for females})$	Serum Cr: Cr Clearance:	Date:
13. If not receiving anticoagulants: International Normalized Ratio (INR) OR Prothrombin (PT) $\leq 1.5 \times \text{ULN}$ If on anticoagulant therapy: PT must be within therapeutic range of intended use of anticoagulants	ULN: INR: PT:	Date:
14. If not receiving anticoagulants: Activated Partial Thromboplastin Time (aPTT) $\leq 1.5 \times \text{ULN}$ If on anticoagulant therapy: aPTT must be within therapeutic range of intended use of anticoagulants	aPTT:	Date:
15. Left ventricular ejection fraction (LVEF) $\geq 40\%$	LVEF:	Date:
16. Women of childbearing potential (WOCBP): negative serum pregnancy test	Serum:	Date:

Contraception

17. Agreement by females **and** males of childbearing potential* to use a highly effective method of birth control or abstain from heterosexual activity for the course of the study through at least 2 days after the last dose of acalabrutinib for females, and at least 4 months after the last dose of ublituximab or umbralisib, whichever comes later, for both men and women. Highly effective methods of birth control are defined in [Appendix K](#).

* Childbearing potential defined as not being surgically sterilized (men and women) or have not been free from menses for > 1 year (women only).

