14.5 Expedited Reporting

Table 14.5 indicates what events must be reported expeditiously.

Table 14.5 Criteria for Expedited Reporting

Time point	What to report
From signing of the consent to study completion	
• All UPs
From signing of the consent to treatment initiation	
• All SAEs
For the time period beginning at treatment through 30 days following cessation of treatment	
• All SAEs* regardless of relationship to protocol therapy• All UPs and AEs that meet the definition of a UP• Ventricular arrhythmias (Section 14.2.1)• Abnormal liver function tests (Section 14.2.3)• Overdose of acalabrutinib, ublituximab or umbralisib (Section 14.3.1)• Pregnancies and lactation
From Day 1 of protocol therapy up to 2 days post last dose of acalabrutinib and 30 days post last dose of ublituximab or umbralisib	
• Pregnancies and lactation
Post Safety Follow-Up to removal from study	
• All SAEs* that are considered probably or definitely related to acalabrutinib, umbralisib or ublituximab

NOTE: All events reported expeditiously require follow-up reporting until the event is resolved, stabilized, or determined to be irreversible by the investigator.

The DCC should be consulted prior to ending the follow-up of events that have stabilized.

* Refer to [Section 14.7](#) for guidelines on reporting secondary malignancies to the industry partners.

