APPENDIX K: HIGHLY EFFECTIVE CONTRACEPTION METHODS

Highly effective methods of contraception (to be used during heterosexual activity) are defined as methods that can achieve a failure rate of <1% per year when used consistently and correctly. Such methods include:

- Combined (estrogen and progestogen containing) hormonal contraception associated with inhibition of ovulation, which may be oral, intravaginal, or transdermal
- Progestogen-only hormonal contraception associated with inhibition of ovulation, which may be oral, injectable, or implantable
- Intrauterine device (IUD) or intrauterine hormone-releasing system (IUS)
- Bilateral tubal occlusion
- Vasectomy of a female subject's male partner (with medical assessment and confirmation of vasectomy surgical success)
- Sexual abstinence (only if refraining from heterosexual intercourse during the entire period of risk associated with the study treatments)

Hormonal contraception may be susceptible to interaction with study or other drugs, which may reduce the efficacy of the contraception method.

Abstinence (relative to heterosexual activity) can only be used as the sole method of contraception if it is consistently employed during the entire period of risk associated with the study treatments as the subject's preferred and usual lifestyle. Periodic abstinence (e.g., calendar, ovulation, sympto-thermal, and post-ovulation methods) and withdrawal are not acceptable methods of contraception.

If a contraceptive method is restricted by local regulations/guidelines, then it does not qualify as an acceptable highly effective method of contraception for subjects participating at sites in the relevant country/region.

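### For female participants, mandatory pregnancy reporting ends 30 days after ublituximab or umbralisib, although contraception is required for at least 4 months

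*Combined protocol and SAP*

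**What the plan says.** **Contraception.** Inclusion criterion 17 (section 3.1) asks for contraception for "at least 4 months after the last dose of ublituximab or umbralisib, whichever comes later, for both men and women". The synopsis gives the same length. Appendix K, when it says when abstinence is acceptable, speaks of refraining "during the entire period of risk associated with the study treatments".

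**Pregnancy reporting, female participants.** Section 14.3.2.1 makes a pregnancy immediately reportable from the first dose "up to 2 days post-last dose of acalabrutinib and 30 days post-last dose of ublituximab or umbralisib". Table 14.5 has a row for pregnancies and lactation with the same limits: "up to 2 days post last dose of acalabrutinib and 30 days post last dose of ublituximab or umbralisib". As the table reads, pregnancies and lactation are also listed in a second, general row with a different end: "For the time period beginning at treatment through 30 days following cessation of treatment".

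**After safety follow-up.** From then until removal from study, Table 14.5 lists only SAEs "considered probably or definitely related to acalabrutinib, umbralisib or ublituximab". Unanticipated problems stay reportable to study completion. Pregnancies are not listed for this period.

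**Partners of male participants.** Section 14.3.2.2 requires partner pregnancies to be reported to both industry partners and sets no time limit.

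**What is known of the risk.** Sections 8.1.5.2 and 8.3.4.2 state that the effects of ublituximab and of umbralisib on pregnancy are unknown.

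**The concern.** The protocol asks women to avoid conception for at least 4 months after these two drugs, but it stops asking sites to report a female participant's pregnancy after 30 days. A woman who conceives between those two points has had an exposure that the protocol itself treats as one to prevent, yet no rule requires the site to report the pregnancy or follow it to outcome. Since the documents call the pregnancy effects of both drugs unknown, each such case carries information that the safety record could lose. Women of childbearing potential can enrol: inclusion 3 admits patients from age 18 with del(17p), TP53 mutation or complex karyotype.

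The stake is completeness of a small part of the safety data. The Simon two-stage design, the CR endpoint and the toxicity monitoring rule are not involved.

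**Working it through.** The plan gives no figure for this gap, so there is nothing to reproduce first. The check is date arithmetic.

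**Inputs**
- Contraception: 4 months after the later of the last ublituximab and umbralisib doses (inclusion 17).
- Reporting, dedicated rule: 2 days after acalabrutinib and 30 days after the other two agents (14.3.2.1; Table 14.5). I read this as the later of the two dates.
- Reporting, general row of Table 14.5: 30 days after treatment ends.
- Schedule (section 5.3): 28-day cycles; last ublituximab on day 1 of cycle 24, last umbralisib on day 7 of cycle 25, acalabrutinib daily through cycle 25.
- Month length is not defined. I assume 28 to 31 days and show the range.

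**Step 1. The gap when all agents stop together.** Gap = 4 × month length − 30.

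| Month length | Contraception (days) | Gap (days) | Share of period |
|---|---|---|---|
| 28 | 112 | 82 | 82/112 = 73% |
| 30 | 120 | 90 | 90/120 = 75% |
| 31 | 124 | 94 | 94/124 = 76% |

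If the last dose of all three agents falls on the same day, both Table 14.5 rows end 30 days later, so the gap is 82 to 94 days under either.

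**Step 2. A patient who finishes cycle 25 on schedule, dedicated rule.** Study day = (cycle − 1) × 28 + day of cycle.
- Last ublituximab: 23 × 28 + 1 = 645.
- Last umbralisib: 24 × 28 + 7 = 679.
- Last acalabrutinib: 24 × 28 + 28 = 700.
- Reporting ends at the latest of 700 + 2 = 702, 645 + 30 = 675 and 679 + 30 = 709, so on day 709.
- Contraception ends on day 679 + 120 = 799 (791 to 803).
- Gap: 799 − 709 = 90 days (82 to 94).

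**Step 3. The same patient, general row.** Reporting ends on day 700 + 30 = 730. Gap: 799 − 730 = 69 days with 30-day months (61 to 73 across the range), or about 70.

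**Step 4. Acalabrutinib continued beyond cycle 25.** Under the dedicated rule the window stays open until 2 days after the last acalabrutinib dose. The gap is zero once that dose falls on or after day 791 − 2 = 789 (801 with 31-day months). That is (789 − 700)/28 = 3.2 to (801 − 700)/28 = 3.6 further cycles. Under the general row it closes sooner: (791 − 30 − 700)/28 = 2.2 to (803 − 30 − 700)/28 = 2.6 cycles.

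**Step 5. How many pregnancies this could concern.** Maximum accrual is 27 (section 12.3), and section 2.1.1 puts the disease at two men to one woman, so about 27/3 = 9 women. Appendix K sets a failure rate below 1% per year for correct use. If all 9 were of childbearing potential, the expected number in a 90-day gap would be below 9 × 0.01 × 90/365 = 0.02 for the whole trial. Imperfect use of contraception would raise this. The stated average age at diagnosis of 68 would lower it.

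**The case against.** The strongest reply is that the gap is narrower than the two intervals suggest, and rarely entered.

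- **Other routes exist.** Section 14.3.2.1 asks for abnormal outcomes and newborn deaths to be reported as SAEs, and for later infant deaths suspected to be linked to in utero exposure. Unanticipated problems are reportable to study completion, and section 14.4 collects AEs until participation ends. This stands in part. After safety follow-up Table 14.5 expedites only SAEs judged probably or definitely related, and nothing says that a pregnancy is in itself an unanticipated problem. An uncomplicated pregnancy has no trigger by any of these routes.
- **Table 14.7 has no end date.** True, but it sets how fast and in what form a report goes to the industry partners. It does not extend which female pregnancies a site must report.
- **Longer windows may apply.** The general row and continued acalabrutinib do shrink or close the gap, as Steps 3 and 4 show. Neither helps a woman who stops everything at once.
- **Numbers are tiny and detection is limited.** This stands. The calendar schedules pregnancy tests only at screening and cycle 1 day 1, and after the 30-day visit the next planned contact is at six-monthly follow-up. A longer window obliges a site to report what it learns; it does not ensure that the site learns of it.
- **No rule makes the two windows equal.** Also true. Treating the 4 months as Appendix K's period of risk is an inference, although inclusion 17 is the only place where the length of contraception for these two agents is set.

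A reader might go further and infer that pregnancies in general go unreported after 30 days, or that partner pregnancies need the same window. The documents do not support this. Section 14.3.2.2 has no cut-off, so giving it a 4-month limit would shorten an open-ended duty. Nor can one say that every exposed pregnancy in the gap is lost, given the SAE and unanticipated-problem routes.

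**Conclusion.** The mismatch is real for female participants and minor in effect. It is widest, at 82 to 94 days, for a woman who stops all agents at about the same time. For completion of cycle 25 on schedule it depends on which Table 14.5 row governs, and it vanishes with roughly 3 to 4 more cycles of acalabrutinib. What it leaves uncovered is chiefly the uncomplicated pregnancy conceived inside it.

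This rests on months of 28 to 31 days, on reading the dedicated rule as the later of its two dates, and on on-schedule dosing for the cycle 25 example. The share of about 75% describes the widest case and should not be quoted as typical. No efficacy analysis or error rate is affected. I take no position on which interval is clinically right; the passages have to be reconciled.

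**What to change.** Reconcile inclusion 17, section 14.3.2.1 and both pregnancy rows of Table 14.5:

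1. The sponsor confirms the contraception period after ublituximab and umbralisib.
2. Section 14.3.2.1 and Table 14.5 then state that reporting of a female participant's pregnancy runs at least to the end of that period. If the present 4 months is confirmed, the gap falls to zero.
3. The two pregnancy rows of Table 14.5 are merged, or given the same end point, so that sites have one rule.
4. Section 14.3.2.2 is left unchanged.

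The cost is a wording amendment to one section and two table rows, plus inclusion 17 and the synopsis if the confirmed period differs from the present text. Added reporting should be negligible given the numbers in Step 5. No extra visits or tests are needed for this change.
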